Summary description of the investigational device and its intended purpose:	
The investigational device, [REDACTED] [REDACTED] is a passive microprocessor-controlled prosthetic knee. It is a Class I product and is a further development of a well-established technology.
 
The device is classified as an "External assembled lower limb prosthesis" according to Title 21 §890.3500, bearing the product code ISW (Assembly, Knee/Shank/Ankle/Foot, External)
 
It is 510(k) exempt, except for general requirements.
 
It is composed of a microprocessor-controlled prosthetic knee, a power supply and a configuration software. [REDACTED] [REDACTED] [REDACTED] [REDACTED] [REDACTED] [REDACTED]
 
The investigational device supports prosthetic use from simple locomotion to ambulation with variable cadence and traverse of various terrains. Additionally, it offers features as step-over-step stairs and ramp walking, running, and cycling.
 
Exo-prosthetic devices are by their nature non-invasive. The investigational device is a non-sterile, reusable (i.e. non-disposable), single user device, which is used as part of prosthetic system.
 
The Investigational device is a programmable electrical medical system (PEMS). Its essential performance is defined as structural support, as loss of structural support does not allow the device to fulfill its intended use. Loss of the PEMS related operation on the other hand allows the user to continue walking even if the performance and feature set provided by the device are reduced.
 
The Investigational device is an internally powered device when operated in its intended medical purpose.
 
Device Intended purpose:
 
The Investigational device is intended as part of a prosthetic system that replaces knee function of a missing lower limb.

Manufacturer of the investigational device:	Össur hf. [name]
Name or number of the model/type, including	Model: NAVII [REDACTED]

[figure not shown]
software version and accessories, if any, to permit full identification:	
Traceability during and after the investigation:	Investigation Device Management Form (IDMF) will be used to track the use of each device within the clinical investigation using the device serial number.

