Intended purpose of the investigational device in the proposed clinical investigation:	
Intended purpose of the investigational device in the proposed clinical investigation is within the intended purpose as described above.
 
See following chapters on the intended purpose of the investigational device in the proposed clinical investigation for details.

The populations and indications for which the investigational device is intended:	
Indications for use: Lower limb amputation(s).
 
No contraindications for use are known for the investigational device.
 
Intended patient population:
 
Medical conditions: Unilateral transfemoral / knee disarticulation amputation;
 
Activity Level: Moderate to high-active ambulators
 
Community ambulators;
 
Ambulation exceeding basic ambulation needs or skills.
 
Impact Level: Low to high impact levels.
 
User Weight: Higher than 45kg;
 
Lower than 136kg (110kg for high impact use).
 
Description of the investigational device:	See Table 3 below for descriptions of device features and their relation to the investigation.

Figure 1 Rheo Knee 4/Navii final product

The investigational device is composed of a microprocessor-controlled prosthetic knee, a power supply and a configuration software.

[REDACTED]

[REDACTED]

[REDACTED]

[REDACTED]

[REDACTED]

[REDACTED]

The aspect of the prosthesis that is in direct physical contact with the amputee is usually a liner that serves as an interface between the amputee and the rest of the prosthesis. In other words, the device is usually not in direct physical contact with the amputee.

As described above, the device is intended to be in contact with intact skin only.

The device does not incorporate, as an integral part, a substance or human blood derivative and is manufactured without utilizing tissues of animal origin.

Summary of the necessary training and experience needed to use the investigational device:	
Training requirements for subjects and procedures relating to fitting and use of a device will for all general purposes be equivalent to the training and procedures required for using a FDA approved/CE-marked device of a similar type. The device should be supplied and fitted by a certified CPO/CO/CP.
 
For the purpose of this investigation training for subjects will be standardized to assure that all subjects will receive the same training.

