The Six Minute Walk test (6MWT) is simply a record of the distance traveled by a given patient at his or her self-selected walking speed over a period of six minutes. All that is required is a stopwatch and a walking corridor or track of known distance^{16,17}.

The Amputee mobility predictor (AMPro) is a 20-item scale that was originally developed to provide a more objective approach to the assignment of Medicare K-levels. The scale includes tasks intended to assess sitting balance, transfers, standing balance, gait, and obstacle negotiation and takes around 15 minutes to administer¹⁷.

The Prostheses Evaluation Questionnaire (PEQ) measures prosthetic-related quality of life. It consists of 82 items grouped into nine subscales. In addition, there are individual questions not contained in the subscales regarding satisfaction, pain, transfers, prosthetic care, self-efficacy, and importance¹⁸. This study will include a set of subscales from the PEQ, including specific questions on descending activities.

L-test of functional mobility is a modified version of the Timed up and go test (TUG) developed for more active lower limb amputees. The patient begins the test seated in a chair, ideally positioned in an exam room and facing the entrance to the hallway. The patient rises from the chair, walks three meters into the hallway, turns 90 degrees and then walks an additional seven meters down the hallway. Upon completing seven meters, he turns 180

degrees, returns down the hallway, turns 90 degrees to face the exam room, and returns the three meters to his chair, where he retakes his seat¹⁹

The Plus-M is a self-report instrument for measuring mobility of adults (age 18+) with lower limb amputation who have experience of using a prosthesis. PLUS-M measures prosthetic users' mobility (i.e., their ability to move intentionally and independently from one place to another). The questions assess respondents' perceived ability to carry out specific activities that require use of both limbs. PLUS-M questions cover movements that range from basic ambulation such as walking a short distance indoors to more complex outdoor activities such as hiking for long distances^{20,21}.

Usability questionnaire: In-house generated questionnaire on specific features in the investigational device e.g. water proof, interaction with the app, running and cycling mode.

Video

Data logging by Össur Logic

Qualitative interview

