For Phase I, 17 subjects are to be enrolled and therefore **20** investigational devices will be used, as the devices are intended to be used by a single patient; one for each subject. The number of 20 investigational devices includes replacement units in case of failure.

For Phase II, the number of investigational devices will depend on the sample size, which will be determined using data from phase I.

● Subjects

All subjects will be dispositioned as follows:

- Screen Failure: Subject did not pass screening procedures, not called in for clinical visit;
- Candidate for enrollment: Passed screening procedures, accepts to come in for clinical visit;
- Enrolled: Subject signs informed consent and takes part in the first experimental session;
- Fitted: Subject leaves the clinic on the investigational device;
- Drop-out: Enrolled subject whose participation ended because they did not want to continue participation.
- Discontinued: Candidate for enrollment or Enrolled subject whose participation ended because they withdrew consent, were withdrawn by the Investigator, were lost to follow up, or died.

Table 7 Inclusion/Exclusion criteria

Inclusion: Only patients with the following characteristics are eligible for study entry:	Exclusion: Patients with the following characteristics are not eligible for study entry:
-45Kg < body weight < 136Kg	-Users with stump pain*
-Cognitive ability to understand all instructions and questionnaires in the study;	-Users with socket problems**
-Unilateral TF/KD amputees that are regular prosthesis users for at least 3 months	-Pregnant Users
-Current MPK users (passive MPKs only)	-Users using Power Knee, Kenevo or mechanical knees as their prescribed prosthesis
-Age \geq 18 years	-Alignment that cannot be matched with the Rheo Knee 4 setup, as described in Instructions for use.
-Willing and able to participate in the study and follow the protocol	-Osseointegration
-Moderate to high active users (PLUS M T-score > 40 ²¹)	

*Question on pain affecting their functional ability (yes/no)

**Socket fit: Socket fit comfort score over 5

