Each device designed and manufactured by Össur is subjected to thorough risk assessment, analysis and control, with failure mode effect analysis and hazard analysis, according to PR-00032 Risk Management process, based on ISO 14971 █ (Risk Management for Medical Devices). All changes performed to the software and/or functions of a device are submitted to multi-level verification and, as applicable, validation processes before being authorized for use in a clinical investigation.

The FMEA and hazard analysis are tools for identifying harms, the sequence of events, their probability, and the potential failures that can cause these harms. Anticipated adverse device effects and residual risks associated with the investigational device, are identified in the Hazard Analysis Documentation █ and Chapter 7 in the Clinical Investigator's Brochure █.

The design criteria are an important input in the risk analysis but also the experience of existing products of similar function and/or type (Post market surveillance data). The Rheo Knee 3 (incl. XC configuration) is an equivalent device currently marketed by Össur; post-market surveillance reporting provides data on device related risks as experienced in the real-world application of the device:

Outcome from Post Market Surveillance (PMS) data has not given reason to update risk management documents. No new harm has been identified from the PMS data and results from analysis do not impact conclusion on final risk assessment.

The following reasonably foreseeable misuses have been identified based on current knowledge about transfemoral prosthetic devices and microprocessors-controlled prosthetic knees.

- Use of product by user exceeding the maximum user weight.
- Use of product by user not meeting the minimum user weight.
- Failure to properly maintain the product and/or maintain the product to the expected level of cleanliness.
- Product contamination by foreign substances or operation of the product in dirty or dusty environments.
- Failure to follow recommended or mandatory service schedule.

- Use of the product over the specified maximum life duration.
- User does not read user manual.
- User cannot read user manual.
- User's clinician is insufficiently trained.
- User receives insufficient training from clinician(s).
- Memory failure (user forgets clinicians' training/advice).
- Nascent Error (user performs well meant "optimization", short-cut or improvisation to unusual circumstances).

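### Table 2 lowers the upper weight limit to 110 kg for high impact use, but the eligibility criteria carry only 136 kg and no readable criterion covers impact level

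*Combined protocol and SAP*

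**What the plan says.** The Summary and Table 7 (under Subjects) give the same weight criterion, "45Kg < body weight < 136Kg", with no qualifier. The activity criterion in both places is "Moderate to high active users", defined by a PLUS-M T-score above 40. It has a floor but no ceiling. None of the other inclusion or exclusion items refers to impact level.

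Table 2 (Investigational Device) describes the intended patient population in more detail. It includes "Impact Level: Low to high impact levels" and gives the upper weight limit as "Lower than 136kg (110kg for high impact use"). High impact use is thus within the intended population, but with a lower weight limit than other use.

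The primary objective, under Objectives and Hypotheses, is restricted to moderate to high active users inside the device's intended population.

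On likely use, Table 2 says of the device that "it offers features as step-over-step stairs and ramp walking, running, and cycling". The in-house usability questionnaire, described under Design of the Clinical Investigation, covers "water proof, interaction with the app, running and cycling mode".

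**The concern.** Two parts of one protocol describe who may use the knee, and they differ by one condition. A site that follows Table 7 to the letter has no prompt to ask about impact level. It could enrol, fit and send home for three weeks a person whom Table 2 places outside the intended population.

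Two things are at stake. The first is exposure. Table 2 names structural support as the device's essential performance, so a load-related weight condition should be visible at the point of entry. The second is the scope of the conclusion. The objective speaks for the intended population, and such a subject would contribute data from outside it.

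**Working it through.** No figure in the plan needs to be reproduced. The check is a comparison of text.

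**Step 1. Apply both rules to the possible cases** (other criteria assumed met).

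| User | Table 7 and Summary | Table 2 intended population |
|---|---|---|
| Above 45 kg and below 110 kg, any impact level | eligible | inside |
| Above 110 kg and below 136 kg, not high impact | eligible | inside |
| Above 110 kg and below 136 kg, high impact | eligible | **outside** |
| Above 136 kg | not eligible | outside |

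The rules disagree in the third row only. A 125 kg user who uses the knee at high impact is an example. A 125 kg user who does not is no problem under either table.

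**Step 2. Look for another provision that would catch the third row.**

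- Table 7 does defer to the Instructions for Use, but only on whether alignment can be matched.
- The Recruitment text mentions telephone screening questions without giving their content.
- Table 8 has no row for weight or impact level. It lists a background questionnaire whose items are not shown.
- The section on the investigational device and comparators has subjects use the knee for daily living as they would any other prosthesis. Risk of Study (To Patient) says the same. Neither limits impact by weight.
- Reporting procedures keeps the prescribed prosthesis at the site during the three weeks, so the subject has only the investigational knee for more demanding activity.
- The Subjects section states that there are no pre-specified criteria for discontinuing a participant.

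Nothing in the readable text applies the 110 kg condition at entry or afterwards.

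**Step 3. Ask whether high impact use is plausible in this trial.** Running is an offered feature, the design justification describes running detection as automatic, and the usability questionnaire asks about running mode. That makes it plausible. It does not make it certain, because no procedure in the readable text requires running and the term high impact is not defined there.

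**Step 4. Try to size it.** The expected number in conflict is

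17 × (share of subjects between 110 and 136 kg) × (share of those who use the knee at high impact).

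The documents give neither share. Purely as an assumption, if 10% to 20% of subjects were in the weight band, 17 × 0.10 = 1.7 and 17 × 0.20 = 3.4, so about 2 to 3 people would need to be asked about impact. The number in conflict is whatever part of those answers yes, from none to all. Phase II uses the same procedures with a sample size still to be set, so the gap would carry over unchanged.

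**The case against.** The best defence is that this is a dropped qualifier and not two clashing limits. Table 7 matches Table 2's outer limits exactly, and 110 kg depends on how the knee is used, not on who the person is. A condition on use belongs naturally in training and product literature. A certified prosthetist does the fitting, and Risk Mitigation provides for training, risk information and product literature. The screening questions, the background questionnaire, the instrument appendix, the Instructions for Use and the Brochure are not available to read, and Table 3 is redacted. A control could sit in any of them.

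Much of this stands. It limits how confident one can be and how serious the gap is. It does not remove the gap, because Table 7 is the list of who is eligible and it omits a condition that Table 2 attaches to the intended population.

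The documents do not support several stronger readings that a reader might infer:

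- *Everyone between 110 and 136 kg is wrongly admitted.* The second row of the table in the working shows otherwise.
- *The sentence "Intended purpose of the investigational device in the proposed clinical investigation is within the intended purpose as described above" is breached.* The intended purpose in Table 2 is replacement of knee function within a prosthetic system, and it contains no weight or impact limit. The strain is with the intended population and the objective.
- *High active means high impact.* PLUS-M is described as running from short indoor walks to long hikes, and running is not mentioned.
- *About 29% of the sample is affected.* The arithmetic (136 − 110) / (136 − 45) = 26 / 91 = 28.6% is a share of kilograms, not of people.
- *The risk section already classes this case as misuse.* Device related risk lists "Use of product by user exceeding the maximum user weight", but does not mention the 110 kg condition.
- *The gap threatens early termination in particular.* Reporting procedures ends the trial after any serious device-related event, whatever the subject's weight.

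**Conclusion.** The point holds in a limited form. The eligibility criteria omit a condition that the protocol's own statement of the intended population contains. A user above 110 kg who uses the knee at high impact would meet the Table 7 weight and activity criteria and still fall outside the population named in the primary objective.

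The number affected is unknown and may be zero. No effect on the endpoints or the analysis has been shown. Severity is moderate: this is an internal inconsistency that bears on participant exposure and on the scope of the conclusion, and it is cheap to remove. A reader might want to treat it as a defect that must be settled before the trial can run. The documents do not support that, because the affected group may be empty and a control may exist in material not supplied.

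The conclusion rests on two assumptions: that the 110 kg figure in Table 2 is meant as a condition on the intended population, as its placement suggests, and that no unseen screening item already applies it.

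**What to change.** Reconcile the Summary criteria and Table 7 with Table 2, so that eligibility and intended population state the same weight and impact conditions. How they are reconciled, and which limit governs, is for the sponsor to decide. State what counts as high impact use, so that sites can apply the result consistently.

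At visit 1, before fitting, record body weight and the subject's expected impact level. If the screening questions, Instructions for Use or Brochure already contain a check, cite it in Table 7.

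The cost is wording in two tables, one screening question and one weight measurement. A few users might become ineligible, depending on how the sponsor reconciles the passages.

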	
 -Age ≥ 18 years 	-Alignment that cannot be matched with the Rheo Knee 4 setup, as described in Instructions for use.
	
 -Willing and able to participate in the study and follow the protocol 	-Osseointegration
	
 -Moderate to high active users (PLUS M T-score>40²¹) 	
Procedures:	
There are three scheduled study events. [REDACTED]
 
[REDACTED] At the initial visit, the first study event, for each subject a researcher qualified to obtain informed consent will seat the subject and proceed as described in chapter 13.8 Informed consent.
 
Prior to fitting the subject will be asked to provide feedback on the current prosthesis, by filling in a set of questionnaires (Including background information) and perform functional tests. The users will be fitted within the standard methods of prosthetic fitting, alignment, introduction, training and walking on various terrain.
 
After initial fitting, subjects will receive standard training on the investigational device by a certified prosthetist (the LPI) with support from sponsor investigators. When training is complete, and subjects feel comfortable and safe they will leave the site on the investigational device to use as their primary prosthesis in their daily life for 3 weeks. During this 3 week period the LPI will be in weekly contact with subjects via telephone to check on any issues that may arise.
 
The second visit will be at three weeks after visit 1. During this visit subjects will complete the same functional tests and questionnaires as at visit 1 (excluding background information) on the investigational device, with the addition of a usability questionnaire. They will then be fitted back to their prescribed device.
 
The third visit will be three weeks later. During this visit subjects will complete the same functional tests and questionnaires as at visit 2 (excluding usability questionnaire) on their prescribed device, as well as completing a qualitative interview on their experiences with both microprocessor knee devices.
 
[REDACTED]
	

*Question on pain affecting their functional ability (yes/no)

**Socket fit: Socket fit comfort score less than 5

Table 1 Summary of procedures and visits

	Recruitment phase: 2-4 weeks prior to baseline	Subject visit 1: BL prescribed device	Subject visit 2: FU RK 4/Navii	Subject visit 3: FU Prescribed device

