Potential subjects identified, fitting inclusion/exclusion criteria, by LPI from customer database		X		
LPI calls potential subjects and screens by telephone		X		
Subject signs ICF			X	
Subject fills in background information questionnaire (PIS)			X	
Subject fills in validated questionnaire (PEQ, PLUS-M, ABC)		X	X	X

Subject fitted with investigational device and receives training according to training protocol	X
Subject fills in usability questionnaire for the investigational device	X
Subject is fitted back to their prescribed prosthesis	X
LPI prints out activity report from the investigational device/ prescribed device	X X
Subject completes qualitative interview	X
End of study	X

- Changes from Previous Revision

- Changes for Revision 1.00

Initial release.

● Abbreviations

ADE	Adverse Device Effect
AE	Adverse Event
ASADE	Anticipated Serious Adverse Device Effect
BL	Baseline
CI	Co-Investigator
COI	Coordinating Investigator
CIB	Clinical Investigator's Brochure
CIP	Clinical Investigation Plan
CIR	Clinical Investigation Report
CRF	Case Report Form
DD	Device Deficiency
EDS	Electronic Data capture System
FU	Follow-Up
GCP	Good Clinical Practice
ICF	Informed Consent Form
IDMF	Investigational Device Management Form
IFU	Instructions For Use
IRB	Independent/Institutional Review Board
LCI	Local Co-Investigator
LPI	Local Principal Investigator
LRA	Local Research Assistant
PI	Principle Investigator
PIS	Participant Information Sheet
SAE	Serious Adverse Event
SADE	Serious Adverse Device Event
SCI	Sponsor Co-investigator
SOTA	State-Of-The-Art
SRA	Sponsor Research Assistant
UE	Use Error
UADE	Unanticipated Adverse Device Effect

● Investigational Device

The investigational device is a pre-market device and will be labeled according to regulations concerning pre-marketed investigational devices.

See Table 2 for details on the investigational device.

Table 2 Identification and Description of the Investigational Device

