See Error! Reference source not found. **Appendix I** for details of all instruments to be used and Error! Reference source not found. **Appendix II** for qualitative interview script.

See chapter **10.2 Sample size calculation** and **Table 5** for analysis of variables.

Equipment required for each subject:

- Investigational device (see section □ Investigational device)
- Other components as applicable (prosthetic feet, adapters)
- Tools for fitting
- Detailed protocol
- Case report forms (CRFs) in Smart-Trial – Tablet/computer **OR** Printed out Case report forms (CRFs including instruments listed above)
- Stopwatch/phone for 6MWT
- Markers and a measured corridor/course of known distance for 6MWT and L-test
- Chair for L-test and AMPro
- Measuring tape
- 10cm obstacle for AMPro
- Qualitative Interview script

The equipment used does not require specific monitoring, maintenance, or calibration procedures.

• Investigational Device(s) and Comparator(s)

The subjects will be asked to use the investigational device as their primary prosthesis for **3 weeks**. Individual exposure will differ between subjects. Subjects are expected to use it for their daily living activities as they would with any other prosthesis.

Subjects will evaluate and provide feedback on their exposure of the comparator prior to them being fitted to the investigational device and again after 3 week follow up after completing follow up on the investigational device.

The comparator device **will be any other passive microprocessor controlled prosthetic knee** (excluding Kenevo as it does not have the same intended patient population as the investigational device). They have the same intended use as the investigational device. Furthermore, they are indicated for the same condition and population group. MPKs are widely accepted devices, providing clinical benefits to the user.

Where possible, the subject will be using the remaining part of their current prosthetic system with the investigational device, as it was used with the comparator device. In some cases where a subject is using components from other manufacturers (e.g. feet not validated for use with the investigational device) compatible components will be provided.

No other device, medication or intervention will be used.

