Potential subjects will be identified from the customer base of the Local Principal Investigator (LPI). LPI evaluates, based on previous experience of interaction with and servicing of patients, if a potential participant is **cognitively capable**. If a potential participant fits the inclusion and exclusion criteria the LPI will contact them via telephone. During the telephone call the LPI will verify if they are interested in participating in a study. If interest is expressed at this point they will answer some screening questions and if the eligibility criteria are met an appointment will be made for the clinical visit and signing of the ICF. Questions relating to the duration of the study, number of clinical visits required and the investigational device will be answered.

Potential risk of participating in the investigation will be explained to the subject at this point to the candidate for enrolment.

The LPI will communicate to the study monitor and sponsor co-investigator the number of users he has identified that meet the inclusion criteria and are willing to participate.

- ii) Test procedure**

There are **three** scheduled study events. **Three sites** will be included in the study, **4-10 users** will be recruited at each site. At the initial visit, the first study event, for each subject a researcher qualified to obtain informed consent will seat the subject and proceed as described in chapter 13.8 **Informed consent**.

Prior to fitting the subject will be asked to provide feedback on the current prosthesis, by filling in a set of questionnaires (Including background information) and perform functional tests. The users will be fitted within the standard methods of prosthetic fitting, alignment, introduction, training and walking on various terrain.

After initial fitting, subjects will receive standard training on the investigational device by a certified prosthetist (the LPI) with support from sponsor investigators. When training is complete, and subjects feel comfortable and safe they will leave the site on the investigational device to use as their primary prosthesis in their daily life for 3 weeks. During this 3 week period the LPI will be in weekly contact with subjects via telephone to check on any issues that may arise.

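### The socket-problem exclusion is defined by opposite score cut-offs in the Summary and in Table 7

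*Combined protocol and SAP*

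**What the plan says.** The eligibility criteria appear twice, in the Summary and in Table 7 under Subjects. Both list "Users with socket problems" as an exclusion and mark it with a double asterisk that leads to a footnote.

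- Summary footnote: "Socket fit comfort score less than 5".
- Table 7 footnote: "Socket fit comfort score over 5". The column it belongs to is headed "Exclusion: Patients with the following characteristics are not eligible for study entry".

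The change log, under Changes for Revision 1.00, records only "Initial release".

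The criteria are applied at recruitment. Under Procedures, Recruitment, the local principal investigator telephones candidates, and "they will answer some screening questions and if the eligibility criteria are met an appointment will be made". Under Test procedure, three sites recruit 4 to 10 users each. The Phase I target is 17 subjects.

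The socket score is not among the instruments listed in the Summary or described under Design of the Clinical Investigation, General. That section points to Appendix I "for details of all instruments to be used", but the appendix is not in the supplied text.

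**The concern.** An eligibility threshold has to be a single rule. Here one exclusion carries two cut-offs that point in opposite directions, and nothing in the supplied text says which page takes precedence or which page the telephone questions follow. Two sites could each follow the protocol and enrol different people. A monitor checking a subject's eligibility could reach either answer, depending on the page consulted.

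Socket comfort could plausibly influence the self-rated endpoints, most directly standing comfort (Table 5, hypothesis 1C), although the documents give no data on this. The rule also carries forward. Phase II is to use the same procedures so that data can be combined, and its priors are to come from the Phase I posterior. An unclear Phase I population would therefore be passed on to Phase II.

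**Working it through.** No figure in the plan needs reproducing. The check sets the two rules side by side and lists which scores each admits, for a candidate who meets every other criterion.

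**Inputs.** The Summary excludes scores below 5. Table 7, as printed, excludes scores above 5. A second reading of Table 7 takes its footnote as the fit required for entry, so that a score above 5 is needed.

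| Score | Summary | Table 7 as printed | Table 7 as entry requirement |
|---|---|---|---|
| Below 5 | excluded | eligible | excluded |
| Exactly 5 | eligible | eligible | excluded |
| Above 5 | eligible | excluded | eligible |

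**Counting scale points.** The supplied text does not give the scale. I assume integer scores and show two ranges.

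- Table 7 as printed, 0-10 scale: the verdicts are opposite at 0 to 4 (5 scores) and at 6 to 10 (5 scores), so 5 + 5 = 10 of 11.
- Table 7 as printed, 1-10 scale: they are opposite at 1 to 4 (4 scores) and at 6 to 10 (5 scores), so 4 + 5 = 9 of 10.
- Table 7 as entry requirement, either scale: they are opposite only at 5, so 1 of 11 or 1 of 10.

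The two excluded sets as printed have no score in common, and the only score admitted by both is 5.

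**Possible share of one site.** With 17 subjects, three sites and at least 4 per site, the largest site can have 17 − 4 − 4 = 9 and the smallest 4. One site working from the other page would supply between 4/17 = 23.5% and 9/17 = 52.9% of the sample. This bounds the number of subjects screened under a different rule. It does not count subjects wrongly enrolled, which cannot be estimated because the documents give no distribution of scores.

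**The case against.** The best answer is that one footnote is a drafting slip and that no site would apply Table 7 literally. The row concerns socket problems and the measure is a comfort score, so a reader would naturally take low scores as the problem. The neighbouring single-asterisk footnote, on pain, names how the item is assessed and not the answer that excludes. The footnotes are therefore not all written as exclusion values, and Table 7 may loosely describe an acceptable fit. The person screening is a certified prosthetist who draws on a known customer base. Site staff are trained, the monitor reviews all data, and the case report forms are checked against the protocol. On this view only a score of exactly 5 is in doubt, and counts of scale points say nothing about how many candidates are affected.

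Much of this stands. The milder reading is plausible, the counts are not a measure of impact, and there is no evidence that sites have diverged. But the milder reading has to be inferred and still leaves the pages in conflict at 5. Training, monitoring and form checks all refer back to the protocol, so they cannot settle a point on which it contradicts itself. Appendix I may give the direction of the scale; that would indicate which footnote was intended without making the two pages agree.

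The design also limits the damage. Each subject is their own control, and the plan says: "Where possible, the subject will be using the remaining part of their current prosthetic system with the investigational device". The same socket should therefore usually serve both knees.

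**Conclusion.** The inconsistency is real and must be corrected before enrolment. Both footnotes are complete and legible, belong to the same exclusion, and are current text; no redaction or amendment explains the difference.

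Its size depends on how Table 7 is read: every score except 5 if taken as printed, or a score of 5 alone if taken as an entry requirement. The number of candidates affected is unknown. The scale-point counts rest on integer scoring and an assumed range of 0-10 or 1-10. The site share is conditional on one site using a different page from the others.

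The consequence is confined to who is enrolled, consistency across sites and the population the results describe. I do not claim a bias in the estimated difference between knees, and I take no position on which cut-off is right.

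**What to change.** Before enrolment:

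1. Reconcile the two footnotes so that the same direction and cut-off appear in the Summary and in Table 7, with a score of exactly 5 assigned explicitly.
2. Word the footnote as either the score that excludes or the score required for entry, and say which.
3. State the range of the socket score and which end means a comfortable socket, or cite Appendix I if it gives this.
4. Check that the telephone screening questions apply the same rule at all three sites.

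The cost is low: two footnotes, one added line on the scale, and a check of the screening questions. The choice of cut-off is the sponsor's.
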